8.4.2 Planned Pharmacodynamic and Biomarker Statistical Analyses

Individual biomarkers referred to in the RAP were correct at time of writing, but may not represent the final / definitive list of analytes. The structure / framework of the univariate statistical analyses will be described for a generic biomarker of a given class & proposed sampling scheme. Additional biomarkers would be assigned to the appropriate class & sampling scheme and would be analysed using a similar methodology.

The proposed multivariate analyses / composite endpoints would be modified accordingly if new biomarkers/analytes are assayed and deemed relevant for inclusion.

Additional analyses would use the next available output numbering and changes (additions / planned analyses that were not performed) would be documented in the CPSR.

Several biomarker sampling types will be collected and stored and reporting performed outside of the CPSR and/or SAC deliverable. These have been captured here for completeness and any details on methodology / comparisons would be included in the respective reporting processes.

Pharmacodynamic/Biomarker
General Considerations

 • Imputations described in Section 11.4.2.3 would be applied to the response variables prior to any further activities. • Listings should also display original and any imputed versions of the response variable. • Unless otherwise stated all planned analyses will use the imputed response variable. If the baseline value is imputed then the imputed value will be included in the statistical analyses (and any change from baseline responses will be computed as the change from imputed baseline). Only if there are many time points and dose levels with imputed values will sensitivity analyses be performed (e.g. by re-fitting the statistical model without the imputed data points). Any sensitivity analyses will be described in the CPSR (separate outputs from these sensitivity analyses may not be included in the final CPSR if the conclusions from the original statistical analysis do not change). • Each of the biomarkers will be examined to determine if a log transformation should be applied prior to any statistical analyses (no outputs will be produced from this step). Log base 2 will be used unless otherwise stated (including on any Figures requiring a logarithmic y-axis). Based on previous experience with biomarker data the default assumption will be that the variable will require a Log base 2 transformation. • If a transformation is necessary then the transformation should be applied to any associated baseline responses prior to them being centred (applies when fitting models using SAS PROC MCMC). • Transformations of the response variable and/or alternative analysis techniques will be explored on an as needed basis if model assumptions appear invalid (these techniques would be documented in the CPSR). • Use will be made of the recommendations contained in the internal DB – Respiratory guidance document on handling PK values below the limit of quantification when summarising the PD data. For the purposes of this study a “large” amount of missing data is defined as $\geq 75\%$ of

Pharmacodynamic/Biomarker

values. For example if the experimental design has 8 potential values for a given time-point and 6 or more are LLQ then selected summary statistics (mean, SD, geometric mean and 95% CI for geometric mean, SD logs and CVb(%) will be set to NA).

- Default sets/layouts of descriptive Summary Tables and Figures will be produced for each biomarker where data permit (these are based on the raw data values and not on statistical model outputs); layouts described below.
- Subsequent statistical analyses will only be performed if the study statistician (or delegate) deems that such analysis may provide additional information / value over and above the descriptive Figures and summary tables (for example, if the majority of responses for biomarker X were below Limit of Quantification on all treatment arms, further statistical modelling are not likely to provide much information and would not be attempted).
- Unless otherwise stated model checking will include examination of Studentised residual plots and Q-Q plots for frequentist based statistical analyses and utilise the techniques in Section 11.11 for Bayesian based analyses.
- Panel plots of selected posterior distributions (using groupings and layouts appropriate to the data being summarised) may also be attempted to bring together the results of (Bayesian) statistical modelling to facilitate easier review to obtain an idea of the behaviour of GSK2245035. These would take the next available display numbers but would not be labelled as post-hoc in their titles because they are summarising existing analyses (the exception to this would be if any of their content utilised modelling results from a post-hoc model).
- Exploratory scatter plots involving different combinations of endpoints (and time points) may be produced to investigate possible correlation structures and biological activity (for example, relating Visit 1 IP-10 fold changes in nasal lavage supernatant to post allergen challenge IL-5 levels at follow up visits). It is not possible to pre-specify these in advance (they will be guided by the observed data). These exploratory scatter plots need not be formally reported unless they are required to support statements made in the CPSR (in which case they would be assigned the next available free number and be labelled as post-hoc). Any subsequent statistical analyses resulting from the exploratory figures would be described in the CPSR and also labelled as post-hoc.

Descriptive data summaries (Figures and Tables)

Figures

- **PD_F1: Displaying Individual Subject level data:** Aim to achieve one page per analyte and treatment combination, containing panels of individual subject data (use judgement on the best layout; expected to be 4 columns and 5 rows but it is allowable to use more than one page if necessary to maintain readability). The x-axis and y-axis ranges should be common across all subjects within the analyte (i.e. Placebo page uses same x-axis and y-axis range as 20ng GSK2245035 page to allow comparability; but different analytes can have different y-axis ranges). The x-axis should be discrete and ordered chronologically. Responses within a visit should be joined but there should be gaps between data points from different visits. Use the colour scheme for the treatment and allergen stratum combination described in Section 11.4.3 for each subject (but do not include a legend). The y-axis should be spaced on an appropriate scale (e.g. Log 2) but the labels can be the untransformed values to allow for greater clinical interpretability. The imputed responses should be displayed. If necessary use abbreviations for labelling visit/time combinations, and footnote accordingly. LLQs and ULQs should be displayed as horizontal dashed lines whenever appropriate (e.g. do not put the LLQ line on if none of the subjects values are near the LLQ value, as it will only extend the y-axis range and make the

Pharmacodynamic/Biomarker

subjects data harder to distinguish). However the corresponding LLQ (and the ULQ if defined) can be displayed in the sub-title (or by line) associated with the graph, even if the reference lines are omitted. Display the analytes in the order given by [Table 13](#). Arrange the subject panels so that they are grouped by allergen exposure stratum, centre and subject ID (if space is constrained each panel label should contain the allergen exposure (P or U) and the subject ID as centre information is implied by the ranges of subject ID numbers). Omit unscheduled data points from these figures (only add an appropriate footnote when required, e.g. "Note: Unscheduled data excluded – see corresponding listing for values")

- **PD_F2: Displaying Individual Subject level data grouped by treatment arm (all timepoints):** Aim to achieve one page per analyte; using a grid layout (Placebo 1st row, 20ng GSK2245035 2nd row). Each column is a visit, arranged chronologically from left to right (try to get all visits on the same page but use more than one page to display visits if necessary). The x-axis and y-axis ranges should be common within each analyte. The x-axis should be discrete and ordered chronologically. Use the colour scheme for the treatment and allergen stratum combination described in Section [11.4.3](#) for each subject. Overlay the means and approximate 95% CI from the corresponding summary tables in thicker lines with different colours; sufficiently offsetting their x-axis values from the individual subject data so that the 95% Cis do not obstruct the individual data markers and/or the other means (if no CI is available due to n* being too low then just plot the mean); i.e. a total of three items to be overlaid; giving the most emphasis to the overall treatment mean. The summary statistics selected should be appropriate to the planned transformations (e.g. if the endpoint is to be log transformed then the mean and associated Cis should be for the geometric mean but if no transformation is planned then they can be for the arithmetic mean). For the individual subject data display the imputed responses using only the planned time-points (omit any unscheduled data). The criteria for y-axis scale/labels, footnotes, LLQ/ULQs and display ordering are the same as PD_F1. The legend should include both i) individual subjects data symbols/line types and ii) the sets of overlaid items (3x means and associated 95% Cis). If the lower and/or upper bound of any CI is negative and the y-axis involves a log transformation then the negative value should be replaced with a suitable small constant (e.g. 10% of the LLQ) and an appropriate footnote added to the display to indicate some of the Cis are altered for display purposes.
- **PD_F3: Displaying Individual Subject level data grouped by treatment arm (Background or Pre-Challenge (or Pre-Dose) timepoints only):** This will use the same principles as PD_F2, except that there are not separate panels (columns) for visits. Instead Visit will form the x-axis categories (ordered chronologically from left to right) and the column label will be the timepoint within the visit (e.g. "Background" or "Pre-Challenge" or "Pre-Dose").
- **PD_F4: Displaying Individual Subject Fold changes grouped by treatment arm (for analytes unrelated to demonstrating TLR7 target engagement):** Aim to achieve one page per analyte, containing panels of individual subject fold-change data; with one panel for each visit/timepoint combination (ordered chronologically from left to right). Within each panel the x-axis is the treatment arm (categorical – ascending dose levels; offset the points by the Stratum level if possible). Use a grid layout; rows contain the reference timepoint (denominator in the fold change ratio) and columns are the visit/timepoint combinations (numerators in the fold change ratio). For example, there may only be one row, which might be labelled as "Pre-BAC for the Visit" and four columns "SV 24h Post BAC", "FUV1 24h Post BAC", "FUV2 24h Post BAC" and "FUV3 24h Post BAC". Use the colour scheme for the treatment and allergen stratum combination described in Section [11.4.3](#) for each subjects fold change value (include this

Pharmacodynamic/Biomarker

information in a legend). Draw a horizontal dashed reference line at 1. If necessary use a log base y-axis.

- **PD_F5: Displaying Individual Subject Fold changes grouped by treatment arm (for analytes related to demonstrating TLR7 target engagement):** This will use the same principles as PD_F4 but will consist of two rows (1st row showing fold changes relative to the true baseline (i.e. before the 1st dose was administered (DV1 Pre-Dose)) and the 2nd row showing fold changes relative to the pre-dose baseline associated with that visit. Note: If i) the timepoint (column) is the reference value in row 2 or ii) no pre-dose value was taken at the corresponding timepoint then the row 2 panel can be left blank/empty.

Tables

- Analytes should be presented in the order described in [Table 13](#). For each analyte the summary statistics should be derived and presented for i) the overall treatments (Placebo and 20ng GSK2245035) and then by ii) the Treatment and Allergen exposure strata combinations (Placebo Presumed, Placebo Unknown, 20ng GSK2245035 Presumed and 20ng GSK2245035 Unknown); each visit and planned time combination (ordered chronologically) within the treatment grouping. The descriptive summary statistics to be presented are detailed in Section [11.4.3](#). Most biomarkers would require log transformations (i.e. the associated tables will also include the geometric means etc). The tables should be modified to include the n* column (see the internal DB – Respiratory guidance document on handling PK values below the limit of quantification). To facilitate presentation with the same layouts use “Overall” for the stratum value when presenting the overall treatment means.

Default approach for Bayesian MCMC Modelling output

Items and Comparisons of interest and required Probability statements for each comparison

- Assuming that the final model is not of the “R1” form (See Section [11.9.1](#)) then treatment comparisons of interest are the equivalents to the frequentist counterpart LSMeans estimates for Treatment*Visit in a model fitted in SAS PROC MIXED. The posterior distributions of these quantities will be obtained and the median and 95% credible interval (equi-tail) will be tabulated and displayed graphically. Additionally, appropriate combinations of model parameters will be constructed to obtain the posterior distributions of the ratio of Active / Placebo for each planned time point (equivalent to extracting out relevant back transformed LSmean diffs from a PROC MIXED call for a log-transformed response variable). The posterior probabilities that the ratios at each planned timepoint exceeded the cut-points described [Table 14](#) will be computed, along with the median and 95% credible interval (equi-tail) of the distribution. The posterior distributions for the ratios will be displayed graphically and the aforementioned items tabulated. Note: These posterior probabilities relate to events in the current study, and the mean responses on the treatment arms. Predictions relating to i) an individual subject in a future trial and ii) the mean response in a future trial with N subjects per arm will not be produced as part of the reporting of this study, but may be obtained as part of experimental design activities for any future clinical trials involving GSK22454035.
- If the model is of the “R1” form (See Section [11.9.1](#)) then the approach will be modified to obtain and display LSMean equivalents of Treatment*Visit*Allergen and the comparisons would be the ratio of Active/Placebo within each Allergen strata within each visit. The same set of default posterior probability cut points will be used for each comparison.

Pharmacodynamic/Biomarker

Table 14 Default Posterior Probability (PP) cut-points of interest for Pharmacodynamic/Biomarkers analyses

Item	X = Treatment ratio (Active / Placebo) at each planned time point
1	PP(X<0.10) "More than a 90% reduction in mean response relative to Placebo"
2	PP(X<0.25) "More than a 75% reduction in mean response relative to Placebo"
3	PP(X<0.50) "More than a 50% reduction in mean response relative to Placebo"
4	PP(X<0.75) "More than a 25% reduction in mean response relative to Placebo"
5	PP(X<0.90) "More than a 10% reduction in mean response relative to Placebo"
6	PP(X<1.00) "Any reduction in mean response relative to Placebo"
7	PP(X≥1.00) "Any increase in mean response relative to Placebo"
8	PP(X>1.10) "More than a 10% increase in mean response relative to Placebo"
9	PP(X>1.25) "More than a 25% increase in mean response relative to Placebo"
10	PP(X>1.50) "More than a 50% increase in mean response relative to Placebo"
11	PP(X>2.00) "More than a 2-fold increase in mean response relative to Placebo"
12	PP(X>10) "More than a 10-fold increase in mean response relative to Placebo"
Note: If the response is untransformed then the cut-points will be computed using the median of the posterior (adjusted) distribution for Placebo and the above ratios to determine the equivalent absolute difference (e.g. If Pbo median = 76 then Item 1 would be PP(Difference (A-P) < -68.4))	
Note: Shortened versions of the labels may be used in the TLFs as appropriate (e.g. PP(X<0.10) or PP(Any Reduction c.f. Pbo))	

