Nasal filter collection	Changes in time (Background timepoint) Direct NAC effects	Nasal Lining fluid	Inflammatory mediators	GSK (Stevenage)	Background Pre-NAC & 6h Post NAC samples only IL-5 IL-16 Conditional: IL-13, IL-33, TSLP, Eotaxin, MDC, TARC, IL-10, IFNg	NAC should increase inflammatory mediators	Treatment related reduction (compared to screening) of either background and or reduction of NAC 6h induced response. Th2 cytokines should all go down if drug is working Th1/Treg cytokines should increase

T&E procedure	"Informal" description / rationale for samples	Matrix	Functional Categories	Vendor (Δ)	Analyte(s)	Comments	
						Anticipated Placebo profile	Characteristics of Successful drug effect
			Mast Cell mediators	GSK (Stevenage)	Pre-NAC & 5m Post NAC samples only Histamine, Tryptase, Conditional:Prostaglandin D2 Note: Data generation conditional on sufficient sample remaining. Would only be assayed if mast cell mediators cannot be detect in Nasal lavage fluid samples	Mast cell mediators should increase in 5 min post NAC sample	Reduction in the NAC (5min/pre-NAC ratio) induced response after treatment compared to the SV

T&E procedure	“Informal” description / rationale for samples	Matrix	Functional Categories	Vendor (Δ)	Analyte(s)	Comments	
						Anticipated Placebo profile	Characteristics of Successful drug effect
Nasal scrape	Changes in time	Nasal Cells	n/a	ZKW	Samples to be held by ZKW, if we are able to get good samples and study is positive will be analysed. Reported outside of CPSR as data generation may take a long time	n/a	n/a
Genetic sample	PGx	Blood	Whole blood	GSK (Stevenage)	Stored for genomic DNA can only be used if individual consent is signed, could be used to see why someone is a non-responder	n/a	n/a
Blood sample for biomarker analysis	TLR7 Induced changes (confirm)	Serum	“TLR7” Target engagement	Q2	IP-10, IFNa, IFNb, IL-1b, IL-6, TNFa, MCP-1	Within visit ratio (24h / Pre-dose) should be approximately one	Increase in within visit fold changes to confirm target engagement

T&E procedure	“Informal” description / rationale for samples	Matrix	Functional Categories	Vendor (Δ)	Analyte(s)	Comments	
						Anticipated Placebo profile	Characteristics of Successful drug effect

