8.4.2.2 Biomarkers Supporting the NAC related exploratory objective(s)

The Background samples should be analysed separately from the others as their intent is to capture changes in condition over the season (longer term changes).

The Pre-NAC, 5min and 6 hours are designed to measure the direct (within day) impact of the NAC procedure. The pre-wash (applied as part of the process to obtain the background sample) should also make the pre-NAC values more consistent (essentially zero) and should ensure that subjects should begin from a similar nasal condition (i.e. with a clean nose). Thus challenge related changes should be more consistent as mediators induced by the challenge should be the dominant items detected.

However, although all post NAC samples may be collected, not all of the biomarker types will be evaluated in the first instance. Pre-NAC samples will be evaluated for all biomarker types (mast cell mediators and inflammatory mediators). Mast cell mediators will also be evaluated from the 5min sample and Inflammatory mediators will be also be evaluated for the 6h sample.

Whilst the statistical analysis may split the data initial summaries will be produced using the complete dataset (i.e. a “PD_F1” format Figure and summarised in descriptive tables).

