11.4.2.3 Imputation for Values Below and Above Limit of Quantification

PD responses which are below the assay's respective lower limit of quantification (LLQ) will be imputed using half of the LLQ value.

PD responses which are above the assay's respective upper limit of quantification (ULQ) will be imputed using the ULQ value.

In the event that multiple LLQ/ULQ values are present the minimum for that analyte (for LLQ) and maximum for that analyte (ULQ) should be used in the imputations. If any LLQ values are zero then a suitable small constant may be used in place, to allow the data to be log transformed (for example half of the smallest observed non-zero value).

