11.6.2.3 Handling of Missing Data for Statistical Analysis

The SAS PROC MCMC framework automatically assumes/implements a missing at random / multiple imputation approach if any of the supplied response variables are missing. This is deemed to be sufficient given the exploratory nature of the study. However, if a large proportion of data are missing then alternative approaches may be considered.

Several analyses are specified as being conditional on there being sufficient non-missing data to take place (e.g. Sputum and biomarkers with large proportions of LLQ values).

If model covariates are missing (e.g. Baseline) then the best approach will be selected on a case by case basis, but may involve omitting the record or imputing a response based on other data prior to fitting the observation model.

Given the exploratory nature of this study and the large number of endpoints it is not possible to pre-specify/cover all eventualities but any missing data approaches investigated would be documented in the CPSR and if deemed important included in the outputs as sensitivity analyses.

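### For biomarker values outside the assay limits, the only sensitivity analysis the SAP names refits the model without them; this is outcome-dependent deletion and cannot test the imputation it is meant to check

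*SAP*

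**What the plan says.** SAP 11.4.2.3 fixes the imputation: "PD responses which are below the assay's respective lower limit of quantification (LLQ) will be imputed using half of the LLQ value". Values above the ULQ are set to the ULQ.

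SAP 8.4.2 (General Considerations) carries this into the models: "Unless otherwise stated all planned analyses will use the imputed response variable". A check follows under a condition: "Only if there are many time points and dose levels with imputed values will sensitivity analyses be performed". The same sentence gives the example, a refit that leaves out the imputed points: "sensitivity analyses be performed (e.g. by re-fitting the statistical model without the imputed data points". No censored-data likelihood and no alternative imputation constant is named. The check is to be described in the study report, but its separate outputs may be left out if the conclusions do not change. The default analysis scale is log2.

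Three other places bear on it:

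- SAP 11.6.2.3 says that PROC MCMC "automatically assumes/implements a missing at random / multiple imputation approach if any of the supplied response variables are missing".
- SAP 8.4.1, Table 12, gives the wanted direction for nasal mediators: "Th2 cytokines should all go down if drug is working". Table 13 lists other analytes (IP-10 and the other TLR7 markers, IgA, IFNg, IL-10) for which a rise is wanted.
- SAP 8.4.2.2 says the nasal pre-wash "should also make the pre-NAC values more consistent (essentially zero").

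**The concern.** A value below the LLQ is not unknown. It is known to be low, and that is the reason it would be dropped. Each arm's mean then comes only from values inside the assay range. Where the drug lowers an analyte, the active arm loses more values than placebo. Setting the points to missing does not help, because missing at random fails by construction when the value itself decides whether it is kept.

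The purpose of the check is to show whether a result from heavily imputed data depends on the LLQ/2 or ULQ constant. A refit with its own bias cannot answer that. Disagreement with the main analysis may come from the deletion, and agreement may only mean that both are biased the same way. LLQ/2 is itself biased once censoring is heavy, so a sound check is worth having.

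**Working it through.** The plan gives no bias or power figure for this point, so there is none to reproduce.

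**From the documents:** LLQ/2 and ULQ imputation (SAP 11.4.2.3), which on the log2 scale puts a low value at log2 LLQ − 1; log2 scale and deletion refit (8.4.2); 20 completers per arm (Protocol 4.3). **Assumed, because the documents do not give them:** normal values on log2, SD 1 to 2, the share of placebo below LLQ, and the true ratios.

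**Level at one time point.** Take placebo mean 0, active mean log2(R), limit L = SD × Φ⁻¹(p), with p the placebo share below LLQ and a = (L − mean)/SD.

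- Deletion: mean + SD × φ(a)/(1 − Φ(a)).
- LLQ/2: Φ(a) × (L − 1) + (1 − Φ(a)) × (deletion mean).

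Example with R = 0.50, SD 1.5, p = 0.40, so L = −0.380:

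- Placebo, deletion: 1.5 × 0.3863/0.600 = 0.966.
- Active: a = 0.413, so 66% lie below LLQ. Deletion: −1 + 1.5 × 0.3663/0.3397 = 0.617.
- Deletion ratio: 2^(0.617 − 0.966) = 0.79.
- LLQ/2: placebo 0.400 × (−1.380) + 0.600 × 0.966 = 0.028; active 0.660 × (−1.380) + 0.340 × 0.617 = −0.701. Ratio 2^(−0.729) = 0.60.

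Over p = 20–40% and SD 1–2, a true 0.50 becomes 0.70 to 0.80 with deletion and 0.50 to 0.62 with LLQ/2.

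For analytes expected to rise (true ratio 2, SD 1–1.5), deleting low values gives 1.30 to 1.60 (25–60% of placebo below LLQ). Deleting high values gives 1.48 to 1.77 (2–10% of placebo above ULQ). These shrink too, although the low values removed there are not suppressed ones.

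**Simulation, true ratio 0.50 only.** 20 per arm, baseline covariate, within-subject correlation 0.6, 400 trials:

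| SD, placebo below LLQ | Deletion | LLQ/2 | Left-censored likelihood |
|---|---|---|---|
| 1.5, 25% | 0.68 | 0.54 | 0.49 |
| 1.5, 40% | 0.74 | 0.60 | 0.50 |
| 1.0, 25% | 0.69 | 0.52 | 0.51 |

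A repeated-measures fit that treats the deleted points as missing at random (150 trials) gave 0.69 to 0.73, so that assumption does not repair the bias.

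**Post/pre fold-change contrast** (the direct BAC and direct NAC models). The same formulas apply to pre and post, with the same SD and LLQ. The screening fold change has the same expectation in both arms and cancels. Example: SD 1.5, 40% of placebo pre-challenge values below LLQ, placebo rise of 2 log2 units, drug halving pre and post alike, so the true ratio is 1.0. Deletion means are placebo 0.966 and 2.180, active 0.617 and 1.477. The ratio is 2^((1.477 − 0.617) − (2.180 − 0.966)) = 2^(0.860 − 1.214) = 0.78, an effect that does not exist.

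| True pattern (25–40% of placebo pre below LLQ, SD 1–1.5) | True ratio | Deletion | LLQ/2 |
|---|---|---|---|
| Pre and post both halved, rise 2 | 1.0 | 0.70–0.78 | 0.82–0.95 |
| Pre × 0.50, post × 0.35, rise 2 | 0.70 | 0.54–0.64 | 0.57–0.65 |
| Only post halved, rise 1 | 0.50 | 0.62–0.70 | 0.48–0.52 |

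With 60–80% of placebo pre-challenge values below LLQ, SD 1.5 and a rise of 2 to 4 units, deletion turns a true 1.0 into 0.64 to 0.86. LLQ/2 is no better there. At 60% and a rise of 2, deletion gives 2^((1.832 − 1.192) − (2.388 − 1.449)) = 0.81, and LLQ/2 gives 2^((0.999 + 0.296) − (1.967 − 0.208)) = 0.73. Both are low, so their agreement would reassure wrongly.

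**The case against.** Much of the case on the other side stands. Deletion is an example, inside a check that runs only when imputation is widespread, on exploratory endpoints. The main analysis keeps every value. SAP 8.4.2 allows other techniques if model assumptions appear invalid, and 11.6.2.3 allows other approaches if much is missing and promises to document them. The SAP does not say that removed points would be coded as missing. It also gives, as a case where no modelling would be done, a majority of responses below the limit on every arm. This would rule out single-time-point scenarios with 60% of placebo below LLQ, so they are left out of the 0.70 to 0.80 range. It might also rule out the 80% fold-change case with a rise of 2, which supplies the 0.86. Sputum cell counts use a constant for zero counts and are outside this rule.

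None of this supplies a valid check. The deletion refit is the only method written down, so it is the one likely to be programmed.

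A reader might go further and infer that the refit removes exactly the values that show suppression, so that a true effect always shrinks towards none and is declared not robust. The documents do not support that. The removed set also holds placebo values, pre-challenge values in both arms and values above the ULQ. In the fold-change models the bias can run the other way. No rule in the SAP makes this check decide robustness, and Table 14 lists posterior probabilities without a decision threshold. Nor does the SAP say that most pre-NAC values will fall below the LLQ; it says only that they should be near zero.

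**Conclusion.** The point holds in a limited form. The named sensitivity analysis selects on the outcome and cannot separate an imputation artefact from a drug effect. For single-time-point levels of an analyte the drug lowers, it is further from the truth than the LLQ/2 analysis it is meant to test. For fold-change contrasts the direction depends on how the drug acts before and after challenge, and either method can be the worse one.

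The sizes rest on assumed SDs, LLQ rates and log-normality. Under that model, the direction for single-time-point levels does not depend on the SD or LLQ rate chosen. Severity is minor: a conditional check on exploratory biomarkers is affected, and no planned main estimate is.

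**What to change.** In SAP 8.4.2, replace the example with wording such as:

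> by re-fitting the same model with values below LLQ treated as left-censored and values above ULQ as right-censored (including baseline values where they are modelled or used as covariates); out-of-range values will not be deleted or set to missing. If the censored model does not converge, the imputation constant will be varied instead (e.g. LLQ and LLQ/4).

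Baselines need the mention because several planned models use a baseline that may itself be below the LLQ. The fallback matters because sampling latent values within unstructured covariance matrices of up to 8×8, with about 20 completers per arm, may not converge.

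The cost is one sentence in the SAP, modest extra PROC MCMC code for the analytes concerned, and possibly convergence work in the larger repeated-measures models. No new data are needed. The censored fit relies on the log-normal model, which varying the constant does not test.
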